**Table 5 Post Dosing Follow-Up Period**

	Study Visit		
	28 Days Post Dosing ±7	56 Days Post Dosing ±7	84 Days Post Dosing ±7
Procedure	Visit window (days)		
Adverse Events Assessment	X	X	X
Concomitant Medication	X	X	X
Urine/Serum Pregnancy Test (WOCBP only)	X	X	X
Pharmacokinetics	X	X	X
Immunogenicity	X	X	X

If the Early Termination (ET) visit occurs within the same timeframe as a Post Dosing visit, the ET assessments should be completed over the Post Dosing assessments.

## 6.2 Other Information for Study Visits

Unscheduled procedures may be required in addition to the procedures detailed above for subject safety and/or exacerbation assessments. The additional procedures are at the discretion of the Investigator. The details of these unscheduled procedures will be recorded in the source documents and entered into the eCRFs.

## 6.3 Safety Assessment Description

### 6.3.1 Medical History, Physical Examination, Height and Weight

Medical history, including UC history, will be collected at the Screening Visit.

The Investigator will perform a complete physical examination at the Screening Visit and at the at the Week 12/Early Termination (ET), Week 50/ET, and yearly thereafter, at a minimum. The complete physical examination must include the following:

- General appearance
- Hair and skin
- Lymph nodes
- Head
- Eyes
- Ears, nose, and throat
- Neck
- Respiratory
- Cardiovascular
- Abdominal
- Musculoskeletal
- Mental status
- Neurological

Unless otherwise indicated, following screening visit, physical examinations should be targeted (symptom directed). Complete and targeted physical examinations are to be performed at specified timepoints according to the schedule of study procedures ([Section 6.1.1](#)).

Height and weight will be measured without the subject wearing shoes. Height (inches or centimeters) will be measured and recorded at the screening visit only and weight (lbs or kg) will be measured and recorded at various timepoints ([Section 6.1.1](#)).

### 6.3.2 Vital Signs

Vital signs to be assessed are heart rate, body temperature, and resting blood pressure. The body position (sitting or supine) should be recorded. Approved medical devices may be used to record these parameters.

### 6.3.3 Chest X-Ray

A chest X-ray (posterior-anterior and lateral views are recommended however local guidelines should be followed) with no evidence of current, active TB or previous inactive TB, general infections, heart failure or malignancy is to be taken at screening or within the 6 months prior to screening and read by a qualified radiologist. Documentation of the official reading must be located and available in the source documentation.

### 6.3.4 Electrocardiogram (ECG)

A standard 12-lead ECG for all subjects will be performed at Screening and at the subsequent visits specified in the schedule of study procedures (Section 6.1.1). The original ECGs with interval printouts and rhythm strip run at 25 mm/sec must be provided as source documentation.

Automatically calculated QT and QTc intervals will be reviewed and checked for gross inaccuracies by the Investigator or designated ECG reviewer. If the automatically calculated QT or QTc intervals are greater than 480 msec, or if either has increased by 50 msec or more over the baseline value, it will be manually over-read by the Investigator or designated ECG reviewer. The ECG parameters that will be assessed include heart rate, PR interval, QRS interval, and QT interval. If QT or QTc interval prolongation exceeding these limits is verified during treatment, the subject's medical background should be examined closely for risk factors that may have contributed to the event, including genotyping for hereditary long QT syndromes, if appropriate.

Any sign of arrhythmia should be noted. During treatment, any indication of QT prolongation or Torsade de Pointes, a polymorphic ventricular tachyarrhythmia that appears on the ECG as continuous twisting of the vector of the QRS complex around the isoelectric baseline, must be recorded as an adverse event and reported to the Medical Monitor.

The decision to continue the treatment of any subject with prolonged QT or QTc interval must be discussed and agreed upon by the Investigator and the Medical Monitor. All such subjects, including subjects with cardiac arrhythmias, should be monitored closely. If appropriate, ECG monitoring should be performed until the QT and QTc interval and waveform morphology have returned to normal. If the prolongation or abnormal rhythm persists, the Medical Monitor must be contacted.

### 6.3.5 Clinical Laboratory Evaluations

Blood and urine samples will be collected and analyzed or tested, according to the standard operating procedures (SOP) of the testing facility, for the following according to the schedule of study procedures (Section 6.1.1):

**Hematology**

- Hemoglobin
- Hematocrit
- Total and differential leukocyte count
- Red blood cell count (with indices)
- Platelet count

**Urinalysis**

- pH
- Specific gravity
- Protein\*
- Glucose
- Ketones
- Bilirubin
- Blood\*
- Nitrite\*
- Urobilinogen
- Leukocyte esterase\*

**Serology**

- HbsAg
- HbcAb
- HIV
- HCV

**Chemistry**

- Blood Urea Nitrogen (BUN)/urea
- Bilirubin (total and direct)
- Uric acid
- Alkaline phosphatase
- Aspartate aminotransferase (AST)
- Alanine aminotransferase (ALT)
- Albumin
- Sodium
- Potassium
- Chloride
- Carbon dioxide/bicarbonate
- Calcium
- Phosphorus (inorganic)/phosphate
- Total protein
- Glucose
- Lactate dehydrogenase (LDH)
- Creatinine
- Creatine kinase (CK)\*\*
- Gamma-glutamyl transferase (GGT)
- Lipid panel (total cholesterol, LDL, HDL and VLDL fractions and triglycerides)\*\*\*

**Other Tests**

- Follicle stimulating hormone (FSH) for postmenopausal females only\*\*\*\*
- QuantiFERON-TB
- Serum/urine pregnancy test (for female subjects only)

\* If urinalysis is positive for protein, blood, nitrite and/or leukocyte esterase, a microscopic examination (for red blood cells, white blood cells, bacteria, casts, and epithelial cells) will be performed.

\*\*CK-MB reflex test (or Troponin 1) may be performed if CK is elevated.

\*\*\*Fasting; refer to schedule of study procedures (Section 6.1.1) for collection time points.

\*\*\*\*If needed

The Investigator must review the screening visit laboratory results for all the measured analytes for each subject prior to Qualification Visit. The subject must not be randomized if any of the laboratory values meet the exclusion criteria or in the opinion of the Investigator, might place the subject at unacceptable risk for participation in this study.

Subjects who would not qualify to participate in the study due to a screening laboratory value abnormality can repeat the test once within the original screening time window without resulting in screen failure, if the Investigator believes there is a reasonable possibility that the subject would be eligible if re-tested.

All subjects with laboratory tests containing clinically significant abnormal values are to be followed regularly until the values return to normal ranges; until a valid reason, other than study drug related AE, is identified; or until further follow-up is deemed medically unnecessary.

### **6.3.5.1 Stool Evaluation**

#### **6.3.5.1.1 Stool Culture**

A stool PCR or culture (per central laboratory or local laboratory availability) is to be performed at the screening visit only and can be performed centrally or locally at the Investigator's discretion. Subjects will be provided with instructions for stool sample collection at home and will be required to submit the stool sample to the site for testing. Ova and parasite examination, if applicable, should be performed based on local guidelines.

#### **6.3.5.1.2 Screening for *Clostridium Difficile***

Highly sensitive screening tests, with high negative predictive value, should be employed in evaluating subjects for eligibility for the study. The detection of *C. difficile* by toxigenic stool culture [stool culture followed by detection of toxin] is considered the gold standard for the diagnosis of the colonization or infection with pathogenic *C. difficile*. Comparable sensitivity may be achieved by direct testing of stool via point of use rapid membrane enzyme immunoassay card for both *C. difficile* toxin A and B and/or glutamate dehydrogenase (GDH) antigen on a card. Use of the card for point of care screening is encouraged where permitted by local regulation. Molecular techniques such as polymerase chain reaction (PCR) for detection of toxin RNA are also acceptable alternatives.

Subjects who are positive at screening can be retested after the completion of a full course of treatment for *C. difficile* infection.

Refer to the Laboratory Manual for further guidance and instruction for *C. difficile* screening. If using the central lab, as the *C. difficile* PCR may be the screening test, a positive PCR test result with a negative toxin result may reflect infection or colonization, and the Investigator should decide whether PCR positivity reflects infection, in which case, treatment should be administered.

## **6.4 Efficacy Assessment Description**

The 3-component Modified Mayo Score (stool frequency, rectal bleeding, and endoscopy) will be used to evaluate disease activity for primary and secondary endpoints. The Modified Mayo scoring system is a composite index consisting of 3 disease variables (each scored on a scale of 0 to 3, with higher scores indicating greater frequency or severity): stool frequency, rectal bleeding, and findings on endoscopy. The 3-component Modified Mayo Score range from 0 to 9 points and utilize 3 disease variables, with higher scores indicating more severe disease. The 4th component of the Modified Mayo Score, physician's global assessment (PGA, scored on a scale of 0 to 3, with higher score indicating greater severity of disease), will be collected and the fully Modified Mayo Score will be used as an exploratory assessment only. The Partial Mayo score

ranges from 0 to 9 points and utilizes the Mayo scoring system of stool frequency, rectal bleeding, and PGA without the endoscopy subscore. See [Appendix 16.1](#) for a description of Modified Mayo Scoring Assessment.

For the current study, the following definitions will apply:

- The 3-component Modified Mayo Score Clinical Response (Clinical Response) – a reduction from Baseline  $\geq 2$  points and  $\geq 30\%$  in Modified Mayo Score, accompanied by a reduction  $\geq 1$  in rectal bleeding subscore or absolute rectal bleeding subscore  $\leq 1$ .
- The 3-component Modified Mayo Score Clinical Remission (Clinical Remission) – endoscopic subscore of 0 or 1, rectal bleeding subscore of 0, and stool frequency subscore of 0 or 1 and not greater than Baseline.
- Symptomatic remission – rectal bleeding subscore = 0 and stool frequency subscore = 0.
- Endoscopic improvement – Endoscopy subscore  $\leq 1$  with no friability.
- Histologic Remission – Geboes score  $\leq 3.1$ .
- Histologic-endoscopic mucosal improvement – Geboes score  $\leq 3.1$  and endoscopy subscore  $\leq 1$  with no friability.
- Mucosal Healing – Geboes score  $\leq 2B.1$  and endoscopy subscore of  $\leq 1$ .

Every effort must be made to ensure the same evaluator(s) will complete the assessment for each subject. Visits should be scheduled with the availability of the evaluator(s) taken into account. If the evaluator(s) is unable to complete the evaluation, then a qualified individual, with overlapping experience may perform the evaluation. Documentation of who performed the evaluation is to be recorded in source notes.

The clinical assessor(s) should be a different person from the one preparing the study medication infusion. Personnel cannot have been involved in preparing study medications in one visit and serve as an assessor at another visit.

A study specific video capture kit, which includes the Endoscopy Video Instructions Manual and other Quick Reference materials, and a detailed Biopsy Procedural Manual will be provided by the central vendor.

#### **6.4.1 Modified Mayo Scoring System**

The Modified Mayo Scoring system will be reviewed and discussed with the investigational staff at the Investigators' Meeting or other forum as a method of standardizing the grading between the investigational staff. For each of the visit where partial Mayo score or 3-component Modified Mayo score/Total Modified Mayo score is collected, subject should complete the eDiary or paper diary entries at least 7 days immediately preceding each study visit.

The eDiary/paper diary will collect the following information on a daily basis during the study:

- ‘Normal’ number of stools per day (when not having a flare). This question will be asked only at the screening visit.
- Number of times needed to visit the toilet to have a bowel movement (per day).
- Presence of blood in the stools (if any).
- Description of blood in the stools (if any).

eDiary/paper diary entries completed by the subject from the most recent **3 consecutive** evaluable days (or the most recent **4 non-consecutive** evaluable days, if there are no 3 consecutive evaluable days available) during the preceding 7 days prior to the visit will be used to calculate the Mayo score. For Day 1/Week 0, subject should not be randomized unless there are adequate evaluable symptom days (3 consecutive evaluable days or 4 non-consecutive evaluable days during the preceding 7 days). Note that symptoms on days of the bowel preparation, endoscopy, and 2 days post endoscopy are not considered evaluable.

Each subject serves as their own control to establish the degree of abnormality of stool frequency. The physician’s global assessment acknowledges the three other criteria (i.e., stool frequency, rectal bleeding, and endoscopy subscore where Mayo score is required), the subject’s daily recollection of number of stools per day and presence of blood in the stools, as well as other observations, such as physical findings and subject’s performance status.

The PGA used to determine the Modified Mayo score must be performed by a Doctor of Medicine (MD), Doctor of Osteopathy (DO), Physician’s Assistant, or a qualified Endoscopist. The physician’s global assessment used to determine the Partial Mayo score may also be performed by a Nurse Practitioner (NP). See [Appendix 16.1](#) for details and calculation of the Modified Mayo score. The PGA will be entered with the electronic data capture (EDC) tool by the investigational site staff. The eDiaries or paper diaries and Mayo Score worksheets will be source documents for this study.

#### **6.4.2 Endoscopy Subscore of the Modified Mayo Scoring System**

The Week 0/Day 1 Visit and Week 12/ET and Week 50/ET will require a 3-component Modified Mayo Score and a Modified Mayo score, both of which include an endoscopy. The Screening, Week 12, Week 50 and yearly endoscopies and bowel preparation should not occur within 2 days before the eDiary or paper diary window (e.g., endoscopy must occur at least 6 days prior to the study visits on Week 0/Day 1). The windows for each of the endoscopy is specified in [Section 6.1.1](#). A Partial Mayo Score is sufficient for all other visits. The Partial Mayo Score will not include the endoscopy subscore since endoscopy is not performed.

The endoscopy performed during Screening should be a malignancy surveillance colonoscopy for subjects who have a diagnosis of UC for  $\geq 7$  years and have not had a screening colonoscopy for  $> 1$  year. In addition, for subjects who have had a diagnosis of UC for  $\geq 7$  years and have been treated in OLE, the Week 50 endoscopy should also be a malignancy surveillance colonoscopy. Subjects should continue to undergo colon cancer surveillance with a full

colonoscopy thereafter as per local guidelines. For all other subjects and all other visits, a sigmoidoscopy **should** be performed, unless a colonoscopy should be performed per standard of care at the site. Regardless of the type of endoscopy performed, only the **30 cm on retraction** of the scope should be used for Modified Mayo scoring purposes (range from 0 to 3 points).

Both the centrally and locally read endoscopy subscores will be used during the study. The central endoscopy subscores will be used to derive the Modified Mayo score for study eligibility. The adjudication of any disagreement between the locally and centrally read endoscopy score will be specified in the central endoscopy reading charter. For purpose of locally read endoscopy subscore, photographs depicting examples of each of the 4 endoscopic subscores will be provided to sites for standardization purposes and the endoscopist should refer to these photos during the procedure to guide assignment of the endoscopy subscore based on best-match to the photos.

### 6.4.3 Collection of Biopsy Samples

During each of the endoscopies (colonoscopy or sigmoidoscopy) performed during the study (during Screening, Week 12, Week 50, and Year 2), biopsies of **8 samples**, 4 at the **most severely affected** and 4 at **an unaffected** (if present) colonic site distal to 30 cm during retraction of the endoscope, will be performed. If the most affected area is ulcerated, the sample should be obtained from the edge of the ulcer. In the absence of any visible lesions characteristic of UC, 4 samples should be collected from the region of 10 cm on retraction of the endoscope. Two (2) of the 4 affected and unaffected biopsy specimens should be placed into the formalin-fixed bottles and 2 of the 4 affected and unaffected biopsy specimens should be placed into the RNAlater solution as indicated in [Table 6](#). The formalin-fixed bottles are pre-filled with 10% neutral buffered formalin and the RNAlater bottles are pre-filled with RNAlater solutions.

**Table 6 Description of Biopsy Sample Collection**

Formalin-fixed		RNAlater	
Affected Area Labeled "Disease"	Unaffected Area Labeled "Normal"	Affected Area Labeled "Disease"	Unaffected Area Labeled "Normal"
2 samples	2 samples	2 samples	2 samples

All samples should be labeled prior to shipment, as instructed in the Laboratory Manual.

All samples will be sent to the central laboratory for the study and processed by a designated central pathology site, which will be blinded to the treatment assignment and endoscopic status. Immunohistochemistry of the formalin-fixed samples may include the following antigens per standard procedure: Foxp3, TL1A, fibrinogen, and DR3. Samples may also be used for study of additional antigens listed above as discovery of new antigens related to the disease become available. Samples will not be stored beyond the end of the study when all analyses have been completed.

#### 6.4.4 Quality of Life (QoL)

Subjects will be asked to complete Inflammatory Bowel Disease Questionnaire (IBDQ) at visits specified in [Section 6.1.1](#) to measure disease specific quality of life. The questionnaires completed by subjects will serve as the source documents for this study.

The IBDQ will be used to measure disease specific quality of life (QoL). The IBDQ is a self-administered 32-item questionnaire that evaluates QoL across 4 dimensions: (1) Bowel – symptoms related to primary bowel disturbance, (2) Systemic symptoms (3) Emotional function and (4) Social function. The response to each question can range from 1 to 7, with 1 indicating severe problem and 7 indicating normal health. The total IBDQ is computed as the sum of the responses to the individual IBDQ questions. The total score can range between 32 to 224 with higher scores indicating a better QoL ([Guyatt 1989](#)).

#### 6.5 Pharmacodynamics

Serum biomarkers will be measured to determine the expression of pro-inflammatory cytokines and other soluble biomarkers that may correlate with UC disease activity. Blood samples for PD are to be drawn at the time points specified in the protocol (see [Section 6.1.1](#)). Stool sample for fecal calprotectin can be collected up to 3 days prior to visit but must be collected prior to any bowel preparation for endoscopy. The actual date and time (24-hour clock time) of each sample will be recorded. Instructions for the handling of the PD samples will be provided in the Laboratory Manual.

Evaluations of pharmacodynamics may include, but are not limited to, the following:

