### 2.3 Exploratory Objectives

- To assess the PK of PRA023 in subjects with UC over time
- To assess the effects of PRA023 on tissue and serum PD markers, including total TL1A concentrations over time
- To assess the effect of PRA023 on inflammatory biomarkers including fecal calprotectin and high sensitivity C-reactive protein (hsCRP) over time
- To assess the proportion of subjects in 3-component Modified Mayo Score response, 3-component Modified Mayo Score remission, endoscopic improvement, Robarts histopathology index (RHI) histologic remission, Geboes score histologic remission, and mucosal healing at Week 50
- To assess the change in Partial Mayo Score over time
- To assess the change in Geboes Index and RHI from Baseline to Week 12 and Week 50
- To assess the exposure-response relationship of PRA023 on PD markers over time
- To assess the proportion of subjects achieving corticosteroid-free-remission at Week 50
- To assess long-term safety, tolerability, and efficacy of PRA023

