## 6.1.1 Schedule of Study Assessments

**Table 1 Schedule of Study Assessments – Screening Period**

Procedure	Study Visit Screening	NOTES
		Screening duration is up to 35 days (5 weeks) *NOTE: for Cohort 2, the 35-day window should start after informed consent and CDx status is known
Eligibility Assessments		
Informed Consent	X	
Inclusion/Exclusion Criteria	X	
Medical and Surgical History	X	
Smoking History	X	
Prior and Current Concomitant Medications	X	
Safety Assessments		
Complete Physical Examination	X	
Interim Physical Examination		
Vital Signs	X	Including height and weight
ECG	X	
Chest X-Ray	X	Must be performed within 6 months of the screening visit with documentation on file.
Adverse Events Assessment	X	
Subject training on electronic diary (eDiary) completion	X	
Issue eDiary to subject	X	
Endoscopy with biopsy	X	Endoscopy should be performed between 28 to 6 days prior to the Week 0/Day 1 visit. Note that subject will need at least 3 consecutive evaluable days or 4 non-consecutive evaluable days of symptoms before Day 1. For subjects who have not had a screening colonoscopy for malignancy per local guideline, a surveillance colonoscopy should be performed. Refer to Section 6.4.2 . Endoscopy should be performed after all other eligibility criteria have been met.
Laboratory Tests		
Pharmacogenomics (buccal swab and blood)	X	For Cohort 2, a buccal swab should be collected and result obtained before all other screening assessments, unless CDx status already known from Study PR100-105
Stool PCR or Culture	X	Can be performed centrally or locally. Ova and parasite examination should also be performed based on local guidelines.
C. difficile PCR/Toxin	X	Can be performed centrally or locally.
Fecal calprotectin	X	To be performed during screening, prior to Week 0/Day 1
CBC	X	
Chemistry Panel	X	
hsCRP	X	
Urinalysis	X	
QuantiFERON-TB	X	Should be repeated if result indeterminate. If indeterminate twice, then either screen fail or be considered for treatment for latent TB, unless deemed not necessary by infectious disease or pulmonary

Procedure	Study Visit Screening	NOTES Screening duration is up to 35 days (5 weeks) *NOTE: for Cohort 2, the 35-day window should start after informed consent and CDx status is known
		specialist. No need to test if negative result available within 90 days of screening.

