**Table 2 Schedule of Study Assessments – Induction Period**

	Study Week	Study Visit							Early Termination	NOTES
		0	2	6	10	12	85			
	Study Day	1	15	43	71	85				
	Visit window (days)	0	±3	±3	±3	±3				
Procedure										
Eligibility Confirmation	X									
Randomization	X								Via IRT system	
Complete Physical Examination						X		X		
Targeted Physical Examination	X	X	X	X	X					
Vital Signs	X a	X	X	X	X	X a		X	Heart rate, temperature, blood pressure; Take pre-dose (no more than 30 minutes pre-infusion), end of infusion, and end of observation period a Weight needed	
ECG	X					X		X		
Adverse Events Assessment	X	X	X	X	X	X		X		
Concomitant Medication	X	X	X	X	X	X		X		
Efficacy Assessments										
Endoscopy with Biopsy						X		X	Endoscopy to be performed 7 or 6 days prior to or within +3 days after the Week 12 visit, or at the early termination visit. Refer to Section 6.4.2.	
Review eDiary Data from Subjects	X	X	X	X	X	X		X	Remind subjects to record in their eDiary daily	
Physician Global Assessment	X	X	X	X	X	X		X		
Partial Mayo Score		X	X	X	X				Include stool frequency, rectal bleeding, and physician's global assessment (PGA)	
Total Modified Mayo Score	X a					X		X	Include 4 components of stool frequency, rectal bleeding, endoscopy from Screening Period a , and PGA	
3-Component Modified Mayo Score	X a					X		X	Include 3 components of stool frequency, rectal bleeding, and endoscopy from Screening Period a	
IBDQ	X					X		X		
Laboratory Testing										
CBC	X		X			X		X		

	Study Visit							NOTES
	Study Week	0	2	6	10	12	Early Termination	
	Study Day	1	15	43	71	85		
Visit window (days)	0	±3	±3	±3	±3	±3		
Procedure								
Chemistry Panel	X		X			X	X	
Fasting Lipid Panel	X					X	X	
Urinalysis	X		X			X	X	
Urine Pregnancy Test (WOCBP only)	X		X			X	X	
Pharmacokinetics	X a	X b	X b	X b	X a	X	X	a. The PK samples at Week 0/Day 1 and Week 10 must be taken pre-dose, and immediately following the end of infusion (within 30 minutes) b. The PK sample taken at Weeks 2 and 6 must be taken pre-dose (within 30 minutes prior to dosing)

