**Table 3 Schedule of Study Assessments – Open-Label Extension Period for 1st Induction Responders**

	Study Visit										NOTES	
	Study Week	14	18	26	34	42	50	Quarterly (Q12w)* Office Visits after Week 50	Early Termination	Infusion Visits (excluding Office Visits)		
Study Day	99	127	183	239	295	351						Note: Subjects who are responders after the First Induction Period proceed to re-randomization at Week 14 *Weeks 62, 74, 86, 98, 110, 122, 134, 146, 158, and 170
Visit window (days)	±7	±7	±14	±14	±14	±14	±14					
Procedure												
Enter subject into IRT for OLE	X											
Complete Physical Examination						X		X a	X			a. Yearly after week 50
Targeted Physical Examination	X	X	X	X	X			X a				a. Except when the yearly complete exam is done
Vital Signs	X	X	X a	X	X	X a	X a		X a	X		Heart rate, temperature, blood pressure; Take pre-dose (no more than 30 minutes pre-infusion) and end of infusion a. Weight needed
EKG			X			X			X			
Adverse Events Assessment	X	X	X	X	X	X	X	X	X	X		
Concomitant Medication	X	X	X	X	X	X	X	X	X	X		
Efficacy Assessments												
Review Diary Data from Subjects	X	X	X	X	X	X	X	X	X	X		Electronic or paper diaries may be used
Physician Global Assessment	X	X	X	X	X	X	X	X	X	X		
Partial Mayo Score	X	X	X	X	X	X	X	X	X	X		Include stool frequency, rectal bleeding, and physician's global assessment (PGA)
Total Modified Mayo Score								X a	X	X		Include 4 components of stool frequency, rectal bleeding, endoscopy, and PGA a. Only if endoscopy is performed
3-component Modified Mayo Score								X a	X	X		Include 3 components of stool frequency, rectal bleeding, and endoscopy a. Only if endoscopy is performed
Endoscopy with Biopsy								X ab	X c	X c		Endoscopy can be performed 14 to 6 days prior to Week 50 and Week 98 visits or within 7 days after Week 50, Week 98, or ET visit

	Study Visit										NOTES	
	14	18	26	34	42	50	Quarterly (Q12w)* Office Visits after Week 50	Early Termination	Infusion Visits (excluding Office Visits)			

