3.1 DEFAULT CDx+

The protocol specified CDx status, called default UC algorithm, was used for stratification of the randomization in Cohort 1. As designed, CDx+ subjects will be enrolled in Cohort 2 following the completion of Cohort 1 enrollment. The analysis for CDx+ related secondary endpoints will be analyzed when all subjects in Cohort 2 complete Week 12 or early discontinue. The combined CDx+ subjects across Cohort 1 and Cohort 2 will constitute the CDx+ FAS for these secondary endpoints.

At the time of this SAP addendum, the planned interim analysis when approximately 80% of subjects in Cohort 1 (i.e., ~96 subjects) have reached Week 12 or early terminated from the study has been completed. DMC reviewed the unblinded interim efficacy and safety data for all available subjects and CDx+ subjects on 19 October 2022. Following the review, DMC recommended to continue the enrollment of Cohort 2, and informed a total sample size of 48 for the cohort.

Based on the emerging information related to CDx development and validation, the Sponsor has made the decision to conduct an additional analysis for CDx+ subpopulation based on Cohort 1 data to assess the effect size of PRA023 in CDx+ subjects. In addition to the subgroup analysis based on CDx status for the primary endpoint, [Table 2](#) lists endpoints that will be assessed for the Cohort 1 CDx+ subpopulation. The methods of analysis are similar to those specified in SAP V01, with the following exceptions:

- The analysis sets are defined as CDx+ subjects who are randomized and treated in Cohort 1.
- No statistical hypothesis testing will be performed between PRA023 and Placebo treatment groups, while 95% confidence intervals will be presented for the estimation of treatment difference.

Table 2 Analyses for CDx+ Population in Cohort 1

Endpoints	Treatment Difference
Proportion of subjects in 3-component Modified Mayo Score clinical remission at Week 12	Included in subgroup analysis of the primary endpoint
Proportion of subjects with endoscopic improvement, as defined by endoscopy subscore ≤ 1 with no friability) at Week 12	Risk difference and 95% CI
Proportion of subjects in 3-component Modified Mayo Score clinical response at Week 12	Risk difference and 95% CI
Mean change in Partial Mayo Score over time Mean change in PRO-2 Score over time	Difference of LS mean and 95% CI
Fold change in hsCRP over time Fold change in fecal calprotectin over time	Ratio of geometric means and 95% CI

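### When endoscopy is done before the Week 12, Week 48/50 or annual visit, no calprotectin stool can satisfy both the 3-day window and the before-preparation rule in Section 6.5

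*Protocol*

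**What the plan says.** Protocol Section 6.5 gives one timing rule for calprotectin stool: it "can be collected up to 3 days prior to visit but must be collected prior to any bowel preparation for endoscopy".

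Endoscopy timing is set elsewhere. For Week 12, the note in Table 2 reads: "Endoscopy to be performed 7 or 6 days prior to or within +3 days after the Week 12 visit". For first-induction responders, Table 3 reads: "Endoscopy can be performed 14 to 6 days prior to Week 50 and Week 98 visits or within 7 days after Week 50". Table 4 gives first-induction non-responders the same range around Weeks 48 and 96. Section 6.4.2 explains the 6-day minimum: endoscopy and preparation must stay clear of the diary days used for the Mayo score.

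Calprotectin is scheduled at these endoscopy visits: Week 12 in Table 2 (as far as its broken columns can be read), Week 50 in Table 3 and Week 48 in Table 4. After that it is six-monthly, so it can fall on an annual endoscopy visit.

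The results are used for the exploratory objective on "inflammatory biomarkers including fecal calprotectin and high sensitivity C-reactive protein (hsCRP) over time" (Protocol Section 2.3) and, in the SAP addendum (Section 3.1, Table 2), for "Fold change in fecal calprotectin over time" in Cohort 1 CDx+ subjects.

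**The concern.** The endoscopy windows were fitted to the symptom diary but not to the stool sample. Section 6.4.1 uses 3 consecutive evaluable diary days and makes the endoscopy day and the 2 days after it non-evaluable. Counting back from the visit, Days -3 to -1 are diary days and Days -5 and -4 are excluded, so Day -6 is the latest pre-visit endoscopy day. That spacing puts bowel preparation well before the 3 days in which stool may be collected.

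A site that scopes before the visit must therefore choose. It can send no stool, send one earlier than the stated window, or send one taken after preparation, which the protocol itself rules out. Sites may choose differently. The calprotectin values would then differ in availability and sampling condition for a reason that lies in scheduling and not in the disease.

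**Working it through.** The plan states no figure for this point, so the check compares the permitted days.

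**Inputs.** Day 0 is the visit.
- Stool day S: -3 to 0, and not after preparation (Section 6.5).
- Endoscopy day E before the visit: -7 or -6 at Week 12 (Table 2); -14 to -6 at Week 48/50 (Tables 3 and 4).
- Endoscopy day E on or after the visit: up to +3 at Week 12; up to +7 at Week 48/50. Day 0 is counted here.
- Preparation day P = E - L. The documents give no lag, so L = 0 (same day) or 1 (day before) is assumed.

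**Condition.** A compliant stool needs a day S with -3 ≤ S ≤ 0 and S ≤ P. The gap between preparation and the opening of the window is -3 - P. If it is positive, no such day exists.

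**Endoscopy before the visit.**
- Latest case, E = -6: the gap is -3 - (-6) = 3 days with L = 0, and -3 - (-7) = 4 days with L = 1.
- Earliest case at Week 12, E = -7 and L = 1: -3 - (-8) = 5 days.
- Earliest case at Week 48/50, E = -14 and L = 1: -3 - (-15) = 12 days.
- Endoscopy days that leave a compliant stool day: 0 of 2 at Week 12 and 0 of 9 at Week 48/50.

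The minimum gap of 3 days does not depend on the assumed lag, because preparation cannot follow the endoscopy and a longer lag only widens the gap.

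**Endoscopy on or after the visit.** The tightest case is E = 0 with L = 1, so P = -1, which still leaves Days -3 and -2 strictly before preparation. Endoscopy days that leave a compliant stool day: 4 of 4 at Week 12 and 8 of 8 at Week 48/50.

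**Does another passage settle it?** Section 6 lets the schedule tables override the text, but the calprotectin rows of Tables 2 to 4 give no stool window. Overlap appears only if the stool window is tied to the nominal date and the visit runs late. At Week 12 that needs a visit 3 days late, endoscopy on Day -6 and same-day preparation. At Week 48/50 it needs a visit at least 3 days late (L = 0) or 4 days late (L = 1). Section 6.5 counts from the visit, so the text does not support that reading.

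**The case against.** **The 3-day clause is a permission.** Section 6.5 says stool *can* be collected up to 3 days before the visit; only the preparation clause says *must*. On that reading, an earlier stool taken before preparation breaks no explicit requirement. This stands in part. But 3 days is the only pre-visit window stated, so an earlier sample has no written support, and sites are left to decide for themselves.

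**Sites can avoid the problem.** Scoping on or after the visit satisfies both conditions. That is correct, and a reader who infers that no compliant Week 12 or Week 48/50 sample can exist for anyone goes too far. The pre-visit option is nevertheless offered on equal terms, with no warning about the stool.

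**Week 0.** Table 1 states: "Endoscopy should be performed between 28 to 6 days prior to the Week 0/Day 1 visit". A reader might infer that every Week 0 stool is non-compliant as well. The documents do not support this. The preparation rule makes sense only for an endoscopy belonging to the same visit; otherwise the screening preparation would bar every later sample too. Week 0 has no endoscopy of its own, and Table 1 gives the screening stool separate timing, before Day 1, so a pre-preparation baseline is available.

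**The stakes are small.** This also stands. Calprotectin is exploratory, no primary or ranked secondary endpoint uses it, and the addendum analysis involves no hypothesis test. Collection date and time are recorded, so affected samples can be identified. SAP V01 and the Laboratory Manual are not among the documents supplied, so whether they contain a sample window or baseline rule cannot be judged.

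**Conclusion.** The rule is wrong as written for one group: subjects whose endoscopy precedes the Week 12, Week 48/50 or later annual visit. Within that group no sample can meet both conditions. This rests on reading the 3-day clause as the collection window and on counting both windows from the actual visit. Outside that group, both conditions can be met.

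The affected share at each visit equals the share scoped before it. The documents give no information on that share, so it could be anything from none to all, and no count of lost samples or loss of precision can be derived. A reader might also infer a biased treatment comparison. That is not shown: assignment in the induction period is randomized and blinded, and nothing links endoscopy timing to arm. What can be expected is missing, out-of-window or post-preparation values in the exploratory calprotectin change and fold-change results. It deserves correction because the correction costs almost nothing, not because any main conclusion depends on it.

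**What to change.** **Wording.** In Section 6.5 and the notes to Tables 2 to 4, state that when endoscopy precedes the visit, the stool is collected shortly before bowel preparation, even if that is more than 3 days before the visit. Keep the 3-day window in all other cases. The Laboratory Manual should say the same.

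**Samples already taken.** Use recorded collection times and endoscopy dates to flag stools taken after that visit's preparation, and repeat the fold-change analysis without them. A stool from Day -3 onward with endoscopy on Day -6 or earlier is post-preparation whatever the lag, so most cases need no preparation date.

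**Cost.** Text changes and one sensitivity analysis; no added sample or visit. The downside is an earlier stool. If it is taken 1 to 2 days before preparation, and preparation is the day before endoscopy, it falls on about Day -10 to -8 at Week 12 (endoscopy Day -7 or -6). At Week 48/50, with endoscopy on Day -14, it falls on about Day -17 to -16, a little over two weeks before the visit. The analysis should use the actual collection date.
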